Control: DEPT; is a local adaption of the Adaptive Process Triage (ADAPT), triage model developed in Sweden in 2006 like most other well-known triage models, was the standard triage model used in the study. It includes the presenting (or chief) complaint in addition to a list of vital signs with cut-off values corresponding to each triage level. These are both registered, and the final triage level is determined by the most urgent triage level assigned Both triage systems identify five levels of urgency with colors (red, orange, yellow, green, and blue). The least urgent of these (the fifth level) was excluded from this study as it is defined as non-emergent patients (e.g. minor injuries) and includes no indication for measuring vital signs.

Aim of the study

The aim of the study is to investigate the impact of I-DEPT that has a systematic involvement of clinical assessment and the possibility to adjust the triage. I-DEPT will be compared to the existing DEPT with a focus on mortality, critical illness/distribution within risk groups and time to assessment

Hypothesis

The main hypothesis is that I-DEPT will be non-inferior to the existing DEPT regarding 30-day mortality.

Timeline

The study will start at October 1, 2020. Due to implementation patients will be enrolled from November 1, 2020 with planned end of inclusion, April 1, 2022. Follow-up will be concluded on May 1, 2022. The primary analysis will be conducted when the last patient has been followed for 30 days and data is available, which is expected to be November 2022.

Study design;

Hospital	1. sep-20	1. okt-20	1. dec-20	1. feb-21	6. april-21	1. juni-21	1. aug-21	1. okt-21	1. dec-21	1. feb-22	1. april-22
Nykøbing Falster Sygehus											
Herlev & Gentofte Hospital											
Sjællands Universitetshospital											
Bispebjerg & Frederiksberg Hospital											
Nordsjællands Hospital											
Slagelse Sygehus, Bomholms Hospital											
Hvidovre & Amager & Glostrup Hospital											
Holbæk Sygehus											
	Baseline										Follow-up
Censureringsperiode											
Studieperiode											
Follow-up periode, 30 dage											

Figure 1: Cluster-randomised step-wedged" design

Note: There was a break between implementation at Bispebjerg og Nordsjaelland

The reason for the break was organisational challenges due to summer holidays with lower staffing in that period.

Inclusion/Exclusion criteria

Eligible Emergency departments

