- 1. Located in the Capital Region or Region Zealand in Denmark
- 2. Arrival of acutely admitted patients at the on-site Emergency department
- 3. Systemised use of Triage

Patient inclusion criteria

1. ≥18 years at contact to participating emergency department

Patients will be included at the first admission in the study period (index admission) and will remain in this group (intervention/control) for a follow-up period of 30 days.

All subsequent admissions (readmissions) will be ignored with regards to treatment group (i.e., you stay in the group you were first admitted into).

Exclusion

- Patients presenting in the ED with minor injuries (e.g. sprained ankle or minor cuts/abrasions) as they are triaged as blue (level 5) in both systems which typically precludes measurement of vital signs
- 2. Patient admitted directly to specialty ward (without contact to the emergency department)

Definition of clusters

Eligible hospitals can consist of one or two units. A hospital is defined based on its administrative organisation and catchment area. Each hospital will generate one cluster and two (time) periods (control and intervention). See schematic figure 1

Randomisation

Prior to the study start participating clusters will be randomised to start as either intervention or control. Eight clusters are available. The randomisation were performed using computer-generated numbers.

Ethics

The study was presented to the Regional Ethics Committee, who decided that no formal approval was needed in accordance with Danish law. Data management has been approved by the Danish Data Protection Agency (ID: P-2022-405).

Data:

The first 30 days after implementation of I-DEPT will be censored to minimize carry over effect. At follow-up (30 days after inclusion of last patient) the following data is collected from the National Patient Registry (NPR) and the electronic patient journal system Sundhedsplatformen:

- Contacts with the hospital system in the trial period.
- Information regarding admissions (date, time and place of admission and discharge, admission disrupted by patient).

- Information on vital signs and triage level
- Diagnoses (follow-up during study period, historical and in relation to index admission).
- Date of death or emigration (only very few cases of emigration are expected).

Outcomes:

Following outcomes are registered at clinicaltrials.gov (NCT04571021) on September 30, 2020

I-DEPT= Intervention

DEPT = Control

Primary outcome:

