• All-cause mortality within 30 days following triage in the index admission by noninferiority (I-DEPT vs. DEPT)

Secondary outcomes

- All-cause mortality within 2 days following triage in the index admission (I-DEPT vs. DEPT)
- Distribution of patients within triage categories (I-DEPT vs. DEPT) including all-cause mortality within 30-days
 - There are four categories in both triage algorithms used in this study: (green (least urgent), yellow, orange, and red (most urgent))
- Patients in the orange triage category (I-DEPT vs. DEPT) including all-cause mortality within 30-days
 - Number of patients assigned to the orange category previous study showed a significant decrease in this patient group
- Doctor assessment (I-DEPT vs. DEPT)
 - Time from triage to arrival of a doctor Note* Timestamp for arrival of doctor need to be discussed
- Length of stay (I-DEPT vs. DEPT)
 - The total number of days admitted to a hospital within 30 days
- Time in the Emergency Department (I-DEPT vs. DEPT)

- Time spent in the Emergency department from triage to either admission, transfer or discharge
- Patients left without being seen (I-DEPT vs. DEPT)
 - Number of patients leaving the Emergency Department without being assessed by a doctor
- Number of admissions to ICU (I-DEPT vs. DEPT) within 24 hours

Additional secondary outcomes – added July 2022

- Days alive out of hospital within 30 days after admission (I-DEPT vs. DEPT)
- Analyses of primary and secondary outcomes will be repeated with 60 days of censoring after implementation.

[figure not shown]
Additional Post-hoc analyses – added January 2023

- Doctor assessment (I-DEPT vs. DEPT) Time from triage to arrival of a doctor – Note* Timestamp for arrival of doctor need to be discussed – divided into triage groups.
- Analyses of primary and secondary outcomes will be repeated with 90 days of censoring after implementation.

Statistical plan for main outcome paper

Consort diagram:

Schematic consort diagram - following will be reported

Baseline description of groups:

Table 1

	I-DEPT	DEPT	P value
Triage: Red (most urgent), n (%)			p=X
Female, n (%)			
Age, years,			
Systolic Blood Pressure, mmHg			
Heart rate, pr. min			
Respiratory rate, pr. min			
Arterial oxygen saturation, %			
Temperature, degrees Celsius			
Triage: Orange, n (%)			p=X
Female, n (%)			
Age, years,			
Systolic Blood Pressure, mmHg			
Heart rate, pr. min			
Respiratory rate, pr. min			
Arterial oxygen saturation, %			

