Temperature, degrees Celsius			
Triage: Yellow, n (%)			р=Х
Female, n (%)			,
Age, years,			
Systolic Blood Pressure, mmHg			
Heart rate, pr. min			
Respiratory rate, pr. min			
Arterial oxygen saturation, %			
Temperature, degrees Celsius			
Triage: Green (least urgent), n (%)			p=X
Female, n (%)			
Age, years,			
Systolic Blood Pressure, mmHg			
Heart rate, pr. min			
Respiratory rate, pr. min			
Arterial oxygen saturation, %			
Temperature, degrees Celsius			
Missing triage			р=X

Table of summary statistics for patients for each group (intervention or control) will be presented for each triage of the four triage groups with baseline variables shown in Table 1.

Continuous variables will be summarized with mean and standard deviation or interquartile range (based on non-missing sample size).

Categorical variables will be reported as frequency and percentages (based on non-missing sample size) and number of missing values.

Categorical variables will be tested with chi-square.

Primary outcome analysis:

The primary outcomes will be an analysis of all-cause mortality within 30 days.

Patients will be followed as one cohort and data will be analysed as randomised and in accordance with the intention-to-treat principle.

- Patients (18+) will be included at the first admission at the participating hospitals in the study period (index admission) and will remain in this group (intervention/control) for follow-up of 30 days.
- Admission is defined as any contact to an emergency department where a Triage is performed
- Any patient lost to follow-up will be censored at the last time known to be alive.

Censored periods: Each period will start with 30 days of implementation, and the end of the study is followed by an observation period of 30 days. Periods of implementation and observation will be censored in the analyses (patients admitted in these periods will not be included in the analyses).

Main analysis

Logistic regression that accounts for clustering with adjustment for hospital ID, age, and sex, period (e.g., calendar month).

Results will be presented with distribution n (%) and Odds Ratio with a 95% Confidens interval and Risk difference with 95% Confidens interval. The assumption is that the actual intervention effect is 0. Non-inferiority will be assessed based on the risk difference with a non-inferiority margin (Δ) of 0.5%.

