Cumulative incidence plots (1-survival) will be calculated using the Kaplan-Meier method and presented with Hazard Ratio and 95% Confidens interval and adjusted for the same variables as the main analysis.

Additional cox regression censoring for "Do not resuscitate order" will also be performed.

Sensitivity analyses of the primary endpoint:

In addition to the ITT analysis, a per-protocol analysis will be performed. In this analysis, interventional patients with missing or incomplete triage will be excluded.

Subgroup analyses of primary endpoint:

The primary outcomes will be calculated for the following subgroups, including a test for interactions.

Results will be presented with distribution n (%) and Odds Ratio with a 95% Confidens interval and illustrated in a Forrest plot and/or Cumulative incidence plots (1-survival) will be calculated using the Kaplan-Meier method.

Following subgroups are planned:

- Triage groups (green to red)
- Age (\leq 39 years, 40 to 69 years, \geq 70 years)
- Medical specialties
- Surgical specialties

Secondary endpoints:

Patients in the orange triage category (I-DEPT vs. DEPT) – including all-cause mortality within 30days:

Main analysis

Same as primary outcome:

Logistic regression that accounts for clustering with adjustment for hospital ID, age, and sex,

period

Results will be presented with distribution n(%) and Odds Ratio with a 95% Confidens interval

Doctor assessment (I-DEPT vs. DEPT)

Time from triage to arrival of a doctor

Main analysis

Distribution will be investigated with Boxplot

Cox regression following the same adjustment principles as for the primary outcome (age, sex, hospital id, period)

Results will be presented with Hazard ratio with a 95% Confidens interval

Length of stay (I-DEPT vs. DEPT)

- The total number of days admitted to a hospital within 30 days

Main analysis

Distribution will be investigated with Boxplot

Linear regression following the same adjustment principles as for the primary outcome (age, sex, hospital id, period?)

Results will be presented with mean days (SD or Interquarentile range) for both groups and difference in hours with a 95% Confidens interval

Time in the Emergency Department (I-DEPT vs. DEPT)

- Time spent in the Emergency department from triage to either admission, transfer or discharge

Main analysis

Linear regression following the same adjustment principles as for the primary outcome (age, sex, hospital id, period?)

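### Assignment to red, yellow and green triage, part of a listed secondary outcome, has no design-based analysis; the only stated test is the unadjusted chi-square in Table 1

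*SAP*

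**What the plan says.** - *Aim of the study* names, beside mortality, "critical illness/distribution within risk groups and time to assessment" as a focus of the comparison.
- *Secondary outcomes* lists "Distribution of patients within triage categories (I-DEPT vs. DEPT) including all-cause mortality within 30-days", covering green, yellow, orange and red.
- *Secondary endpoints*, which sets out the analyses, has no entry for this outcome. It has one for the orange category: "Logistic regression that accounts for clustering with adjustment for hospital ID, age, and sex", plus period. The wording leaves open whether assignment to orange, mortality within orange, or both is modelled.
- *Subgroup analyses of primary endpoint* includes the triage groups, with interaction tests. That covers mortality by colour, not how many patients receive each colour.
- *Baseline description of groups* contains Table 1, with a p-value column. The entry p=X stands only beside the four colours (for example "Triage: Red (most urgent), n" and %) and beside missing triage. Sex, age and vital signs have none. The text below the table adds "Categorical variables will be tested with chi-square".
- The design is labelled "Cluster-randomised step-wedged". *Randomisation* states "Eight clusters are available", and *Definition of clusters* states "Each hospital will generate one cluster and two (time) periods (control and intervention".

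**The concern.** Triage colour is not a baseline characteristic here. It is produced by the system being compared, so a p value for I-DEPT versus DEPT on a colour is a test of a treatment effect, whatever heading it sits under. Followed as written, the plan would report such p values for red, yellow and green with no term for hospital or calendar time and with patients treated as independent.

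In a stepped wedge, DEPT contacts come mainly from early months and late-switching hospitals, and I-DEPT contacts from the reverse. The SAP accepts that this needs adjustment, because the primary and orange models carry hospital and period terms and account for clustering. Orange could therefore end up with both an adjusted odds ratio and a crude p value, and the other colours with the crude p value alone. At stake is whether a reported shift of patients between risk groups can be attributed to I-DEPT.

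**Working it through.** The SAP gives no sample size, category share, between-hospital variance or time trend for this outcome, so there is no stated figure to reproduce. The check shows what the crude test would do under assumed inputs.

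**Inputs from the SAP.** Eight clusters; 30 days excluded after each switch; enrolment from 1 November 2020 to 1 April 2022 (*Timeline*). Figure 1 also has a baseline column from 1 September 2020, so both starts were run.

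**Assumed inputs.** The shading of Figure 1 is not readable. Switch dates were inferred from its column dates, with June 2021 skipped for the stated break: 1 Oct and 1 Dec 2020; 1 Feb, 6 Apr, 1 Aug, 1 Oct and 1 Dec 2021; 1 Feb 2022. Also assumed: equal and constant hospital volumes, a category share of 25%, total N of 20,000 or 100,000, and a true effect of 0.

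**Step 1: imbalance between arms (start 1 November 2020).**
- DEPT days by hospital: 0, 30, 92, 156, 273, 334, 395, 457 (total 1,737).
- I-DEPT days: 516, 456, 394, 330, 213, 152, 91, 29 (total 2,181).
- The four earliest-switching hospitals supply 1,696/2,181 = 78% of I-DEPT time but 278/1,737 = 16% of DEPT time (22% with the September start).
- The mean calendar month is 10.8 for I-DEPT and 5.5 for DEPT, a gap of 5.3 months (6.6 with the September start).

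**Step 2: size of the spurious difference.** One logit unit at a 25% share is about 0.25 × 0.75 = 0.1875 on the probability scale.
- Trend: slope × gap × 0.1875. For 0.01 logit per month, 0.01 × 5.3 × 0.1875 = 0.0099, or 1.0 percentage point; for 0.02, 2.0 points.
- Hospital mix: SD = √Σ(I-DEPT share − DEPT share)² × hospital SD × 0.1875, and the root is 0.478. For hospital SD 0.1 logit, 0.478 × 0.1 × 0.1875 = 0.9 points; for SD 0.3, 2.7 points. The mean is zero, because the switching order is randomised.

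**Step 3: rejection rate of the crude chi-square at nominal 5%, true effect 0** (400 simulations per setting, November start).

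| Trend (logit/month) | Hospital SD (logit) | N = 20,000 | N = 100,000 |
|---|---|---|---|
| 0 | 0 | 7% | 8% |
| 0 | 0.1 | 27% | 55% |
| 0 | 0.3 | 68% | 85% |
| 0.005 | 0 | 10% | 46% |
| 0.01 | 0 | 36% | 94% |
| 0.02 | 0 | 89% | 100% |
| 0.01 | 0.2 | 54% | 81% |

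Hand check for SD 0.1 and N = 100,000: the arms hold 44,334 and 55,666 patients. The standard error that the chi-square assumes is √(0.1875 × (1/44,334 + 1/55,666)) = 0.0028. The actual SD is √(0.0090² + 0.0028²) = 0.0094. The probability of rejection is then 2 × Φ(−1.96 × 0.0028/0.0094), about 56%, against 55% simulated.

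**Step 4: the same data with hospital and calendar-month terms.** Rejection is about 5% overall (2% to 11% by setting, 150 runs each, Monte Carlo standard error about 1.8 points). That model had fixed hospital effects and no hospital-by-period variation. It shows that the confounding is removed; it does not validate inference from eight clusters.

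**The case against.** The chi-square sentence belongs to the baseline table, and the SAP nowhere names it as the analysis of this outcome. The gap may be a plain omission: 2-day mortality, also a listed secondary outcome, has no entry either. This stands, and it is why the point is a missing analysis with an unsuitable test in its place by default. It does not remove the problem, because p=X is reserved for the triage rows, and without those p values red, yellow and green assignment has no stated test at all.

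A reader might infer that the whole outcome is tested only by a crude chi-square. The SAP does not support that, given the adjusted orange model and the mortality subgroup analysis.

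A reader might also infer that the crude contrast compares only seasons and hospitals, so that any shift found could be wholly spurious. That goes too far as well. The two systems assign colours by different rules, so direct relabelling is plausible and the crude contrast contains it. Hospital mix is a chance imbalance with expectation zero, since order was randomised; only calendar time is systematic. The high rejection rates largely reflect a big sample detecting differences of 1 to 2 points.

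Finally, the rates rest on inferred dates and assumed volumes, shares and variances. Equal monthly volumes also ignore that each patient counts once, at first admission. The rates are illustrations, not predictions.

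**Conclusion.** The concern holds in this limited form. Assignment to red, yellow and green is part of a listed secondary outcome and of the stated aim, yet its only stated between-system test ignores hospital, calendar period and clustering. Under the assumptions above, I-DEPT time falls about 5 to 7 months later on average. With hospital SD of 0.1 to 0.3 logit, or a trend of 0.01 logit per month, false rejection is about 27% to 94%. A trend of half that size gives 10% to 46%, one of twice that size 89% to 100%, and with neither source the rate is about nominal. The spurious difference is typically 1 to 2 percentage points, and nearly 3 at the largest hospital variation tried. A large true shift would remain visible, but neither its p value nor its exact size could be attributed to I-DEPT alone. This should be corrected; it does not touch the primary outcome.

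**What to change.** - Add an entry for this outcome under *Secondary endpoints*. Use the primary-outcome model for assignment to each colour (per-category logistic, or one ordinal or multinomial model) with hospital, calendar period, age and sex. Say calendar period explicitly, because *Definition of clusters* uses period for the control and intervention phases.
- State how clustering is handled in a way suited to eight clusters, for example a small-sample correction or a permutation test over the randomised switching order.
- State how missing triage is handled. Table 1 has a row for it, and the general multiple-imputation rule does not say whether it applies to triage colour as an outcome.
- State whether the orange entry models assignment, mortality or both.
- Report adjusted differences with 95% confidence intervals.
- In Table 1, drop the chi-square p values from the triage rows or label them descriptive, and keep n (%).

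The cost is a few lines of SAP text and some extra runs of a model already planned. Intervals will be wider than the crude test implies.

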Results will be presented with mean hours (SD eller Interquarentile range) for both groups and difference in hours with a 95% Confidens interval

Patients left Emergency department without being seen (I-DEPT vs. DEPT)

- Number of patients leaving the Emergency Department without being assessed by a doctor

Main analysis

Analysis – Logistic regression that accounts for clustering with adjustment for hospital ID, age, and sex, period??

Results will be presented with distribution n (%) and Odds Ratio with a 95% Confidens interval

Number of admissions to ICU (I-DEPT vs. DEPT) within 24 hours

Main analysis

Analysis - Logistic regression that accounts for clustering with adjustment for hospital ID, age, and sex, period

Results will be presented with distribution n (%) and Odds Ratio with a 95% Confidens interval

Days out of hospital within 30 days after admission (I-DEPT vs. DEPT)

Main analysis

Distribution will be investigated with Boxplot

Linear regression following the same adjustment principles as for the primary outcome (age, sex, hospital id, period?)

Results will be presented with mean days (SD or Interquarentile range) for both groups and difference in hours with a 95% Confidens interval

Handling of missing data:

The primary outcome analysis should be subject to no or little missing data as it is based on Danish register data. Patients lost to follow-up (tourists) will be censored at the last registration. If more than 5% of data is missing on a variable included in planned analyses, multiple imputation will be introduced.

Additional Post-hoc analyses (planned ultimo July 2022)

Analyses of primary and secondary outcomes will be repeated with 60 days of censoring after implementation.

Analyses of primary and secondary outcomes will be repeated with 90 days of censoring after implementation.

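### The analysis called intention-to-treat admits only triaged ED contacts, while Table 1 and the per-protocol rule presuppose patients with missing triage; population and time zero need reconciling

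*SAP*

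**What the plan says.** All places are in the SAP.

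- **Patient inclusion criteria:** the single numbered criterion is "≥18 years at contact to participating emergency department". The text beneath it includes patients at their first admission in the study period.
- **Primary outcome analysis:** "data will be analysed as randomised and in accordance with the intention-to-treat principle". The bullets that follow add "Admission is defined as any contact to an emergency department where a Triage is performed".
- **Outcomes:** the primary outcome is "All-cause mortality within 30 days following triage in the index admission by noninferiority (I-DEPT vs. DEPT". The 2-day mortality outcome also counts from triage.
- **Table 1:** the last row is "Missing triage", with columns for both arms and a p value.
- **Sensitivity analyses of the primary endpoint:** a per-protocol analysis is run in addition to ITT. "In this analysis, interventional patients with missing or incomplete triage will be excluded".
- **Handling of missing data:** a variable in a planned analysis with more than 5% missing is to be imputed. Triage group is a planned subgroup variable.
- **Patients left without being seen:** "Number of patients leaving the Emergency Department without being assessed by a doctor". Nothing says whether triage must have happened first.

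**The concern.** Triage is the process being randomised. Under the Primary outcome analysis definition, a patient enters the cohort, and the mortality clock starts, only once that process has been delivered. A patient who dies, leaves or goes straight to treatment before triage would then have no index admission. If the same person is triaged at a later contact, that contact becomes the index, possibly in the other arm.

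Other sections treat patients without triage as present. The SAP can therefore be read as excluding them, tabulating them, removing them from one arm only, or imputing their triage level. Two analysts could build different primary populations from it.

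At stake is the 30-day risk difference, judged against a fixed 0.5-point margin. If the untriaged share or mortality among the untriaged differs by arm, conditioning on triage can create or hide a difference.

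**Working it through.** **Step 1: the passages side by side.** The SAP states no untriaged share, mortality rate or sample size, so there is no figure to reproduce.

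- By the definition in Primary outcome analysis, a contact without triage is outside the analysis.
- By the Table 1 row and the per-protocol rule, patients with missing triage are inside the ITT set; otherwise there is nobody to tabulate or remove on that ground.
- The two fit together only if missing means performed but not recorded. The SAP does not say so. Triage level comes from records (Data section), and no rule separates unperformed from unrecorded triage.
- No section gives a time zero for a contact without triage.

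**Step 2: size if the all-contact risk is equal.** From the SAP (Main analysis): margin 0.5 points, true effect 0. Assumed: all-contact 30-day mortality M = 3.5% in both arms; untriaged share u = 3% under DEPT and 1% under I-DEPT; mortality m among the untriaged of 10% or 0.5%.

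Analysed mortality = (M - u × m) / (1 - u)

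- m = 10%: DEPT (3.5 - 0.30)/0.97 = 3.30%; I-DEPT (3.5 - 0.10)/0.99 = 3.43%. Difference +0.14 points before rounding, about 27% of the margin.
- m = 0.5%: DEPT (3.5 - 0.015)/0.97 = 3.59%; I-DEPT (3.5 - 0.005)/0.99 = 3.53%. Difference -0.06 points, about one eighth of the margin.

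Swapping the shares between arms reverses both signs. With equal shares and equal m, the false difference is 0.

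**Step 3: size if the triaged-only risk is equal.** Assumed: mortality in triaged patients m_t = 4% in both arms, so the triaged-only difference is 0; u = 2% under DEPT and 5% under I-DEPT.

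All-contact risk = (1 - u) × m_t + u × m

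- m = 2%: DEPT 3.92 + 0.04 = 3.96%; I-DEPT 3.80 + 0.10 = 3.90%. Difference -0.06 points.
- m = 10%: DEPT 3.92 + 0.20 = 4.12%; I-DEPT 3.80 + 0.50 = 4.30%. Difference +0.18 points.
- m = 20%: DEPT 3.92 + 0.40 = 4.32%; I-DEPT 3.80 + 1.00 = 4.80%. Difference +0.48 points.

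The gap in untriaged share that alone equals the margin is 0.5 / (m - m_t): 5 percentage points when m exceeds m_t by 10 points, and 2.5 when it exceeds it by 20.

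**Step 4: the one-arm per-protocol exclusion.** With m_t = 4%, removing 5% of intervention patients who have 10% mortality takes that arm from 0.95 × 4 + 0.05 × 10 = 4.30% to 4.00%, a shift of -0.30 points in favour of I-DEPT. If those removed have 2% mortality, the arm goes from 3.90% to 4.00%, a shift of +0.10.

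**Step 5: leaving without being seen, only if the triage condition carries over.** Suppose 4% leave unseen in both arms, half of them before triage under DEPT and a quarter under I-DEPT. The outcome would read 4 × 0.50/0.98 = 2.0% against 4 × 0.75/0.99 = 3.0%.

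**The case against.** The strongest reply is that the passages agree once missing triage is read as triage done but not recorded or not completed. Table 1 reporting includes numbers of missing values, which suits that reading. It is possible, and it would turn the contradiction into an ambiguity. But it is not stated, it needs a rule that the SAP lacks, and it leaves entry conditional on triage.

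Four stronger conclusions that a reader might draw are not supported:

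- *Untriaged patients do drop out of the comparison.* The SAP points both ways, so their status is unclear rather than settled.
- *Whether a patient is triaged depends on the arm.* The Short summary describes I-DEPT as simple and quick, which makes a different share plausible. No section says that the share triaged, or the wait for triage, differs.
- *The inclusion criteria take in every adult contact and Primary outcome analysis overrides them.* They already speak of the first admission, require departments with systematic triage and exclude minor injuries by reference to triage level. Eligibility is partly tied to triage from the start.
- *Patients who leave before triage are not counted as left without being seen.* That follows only if a definition placed under the primary outcome carries over to a secondary one.

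It is also fair that every size above rests on assumed inputs, and that in the 3% against 1% case the larger shift goes against I-DEPT. The direction depends on which arm leaves more patients untriaged, so this gives no assurance.

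Finally, the SAP lists mortality following triage as the registered outcome. Replacing that clock altogether would be debatable; the objection stands to that extent.

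**Conclusion.** The point holds as an inconsistency in the analysis population with a possible selection bias. The inconsistency needs no assumption: the ITT label, the triage-based definition, the Table 1 row and the per-protocol rule cannot all be applied without a rule that the SAP does not give.

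The bias is plausible but not demonstrated. It requires the untriaged share, or mortality among the untriaged, to differ by arm. With 3% against 1% untriaged and 3.5% mortality, all assumed, it is about -0.06 to +0.14 points against the 0.5-point margin. A wider assumed gap in share with high mortality among the untriaged could approach the margin, as in the +0.48 case. With no differential it is zero. The SAP should be corrected, but it does not show that the primary comparison is biased.

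**What to change.** - **Population.** Define the ITT set as the first eligible adult ED contact in the study period, allocated by the hospital's period at arrival. Include contacts with missing triage. Leave out direct-to-ward admissions and contacts identifiable as minor injuries, in line with the present exclusions.
- **Missing triage.** State how it is identified in the records, and whether unperformed and unrecorded triage are told apart.
- **Time zero.** Keep the registered triage-based clock for triaged patients and use arrival where no triage time exists.
- **Sensitivity analyses.** Run the clock from arrival for all contacts. Restrict to triaged patients in both arms, rather than removing them from the intervention arm only.
- **Reporting.** Give untriaged contacts and their deaths by arm in the CONSORT diagram. State whether leaving without being seen is counted from arrival.

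**Cost.** SAP wording and a somewhat wider extract. The Data section already lists hospital contacts and the date, time and place of admission; that these give a usable ED arrival time is an assumption. Because inclusion was planned to end on April 1, 2022, the change to the population should be dated and disclosed.

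**Downside.** The data list names diagnoses but no contact reason, so some untriaged minor injuries may enter. That would lower mortality in both arms and can shrink an absolute difference against the fixed margin, so the triaged-only result should be shown alongside.
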